3.8 Selection criteria

The **inclusion criteria** for this study is as follows:

- ✚ A self-reported BQ chewer who has been chewing BQ for the past 6 months with atleast 2-3 chewing episode per week. The ingredient of BQ must include AN without or without smokeless tobacco.
- ✚ Other optional ingredients such as slaked lime and betel leaf are allowed.
- ✚ Age of participant must be 18 year old or above
- ✚ Participants must be residing in study location (Kota Belud, Sabah)
- ✚ Ability to comprehend, converse and read in Bahasa Melayu and their local language (Bajau)
- ✚ Participants who are able to provide written consent and agree to comply with all protocol-specified procedures such as providing saliva samples, participating in five 1-2 hours sessions of intervention over 22 days and agree to attend follow-up sessions on first and third month

The **exclusion criteria** for this study are as below:

- ✚ Non-Malaysian citizen
- ✚ Participants who are not willing to quit the BQ chewing habit at the time of the study
- ✚ Women who are pregnant or nursing at the time of study
- ✚ Individuals with psychiatric illness or special social situations that would limit their compliance with study requirements

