Franke AA et al., in 2016 conducted a pilot study to further explore the pharmacokinetics of AN's alkaloid as those assessment of biomarkers was very in need to evaluate the effectiveness of BQ cessation program that was targeted to reduce the oral cancer burden in the high-risk areas in Hawaii. The study found that AN alkaloids; **arecoline, guvacoline, guvacine, and arecaidine were detected in saliva of all participants and peaked within the first 2 hours post-chewing before returning to baseline levels after 8 hours**. The salivary chavibetol was reported in participants consuming betel leaves in their quid and it peaked 1-hour post-chewing. Thus, the study concluded the AN biomarkers from saliva can be followed up only on a short-term basis (≤ 8 h post-chewing). The study too claimed to find similar AN alkaloids from urine samples of the participants.

Franke AA et al. (2022) reported that **saliva bio verification results are valid to be used to verify the self-reported chewing status of participants ('quitter' or 'chewer') at day 22 follow-up to evaluate cessation program's effectiveness**. In the BENIT trial, among the quitters, the decrease in AN compounds were most significant for arecoline ($p=0.044$), followed by arecaidine ($p=0.042$) and nicotine ($p=0.011$). Among the current chewers, the significant decrease was noted only for hydroxycotinine ($p=0.004$).

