3.12.2 Secondary Outcome Measures

Levels of areca nut biomarkers in saliva samples will be tested via liquid chromatography mass spectrometry at day 22. The cut-off levels for areca nut biomarkers are arecoline (60 ng/mL), arecaidine (10 ng/mL), guvacoline (20 ng/mL), and guvacine (6 ng/mL) and cotinine (10 ng/mL). Biomarkers level above this cut-off points represent that participants are still practicing the habit and have not ceased the habit.

Levels of areca nut biomarkers in saliva samples will be tested via liquid chromatography mass spectrometry at Month-3. The cut-off levels for areca nut biomarkers are arecoline (60 ng/mL), arecaidine (10 ng/mL), guvacoline (20 ng/mL), and guvacine (6 ng/mL) and cotinine (10 ng/mL). Biomarkers level above this cut-off points represent that participants are still practicing the habit and have not ceased the habit.

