3.14 Data Collection

3.14.1 Baseline

The facilitators from the Kota Belud Dental Clinic staff will be trained and standardised for the conduct of this study. A training manual will be given to each facilitators. They will be briefed and their understanding on every item of the questionnaire and worksheets will be scrutinised and refined as intended by the study. Any difficult words identified by the facilitators will be changed to a simpler alternative. Translated words into Bajau dialect will be discussed and decided upon for standardisation.

From face-to-face interviews with the participants, information regarding demographics details and baseline information about BQ chewing behaviour, BQ composition, BQ dependency levels, reasons for chewing and readiness and self-perceived barriers to quit will be garnered. Face-to-face interview mode was chosen as a method to complete the questionnaire to obtain a better response rate and to minimise inaccurate response due to illiteracy issues and participant's poor comprehension due to age.

Participant's baseline saliva samples will be gained for biomarker comparison as a method to verify the intervention's self-reported effectiveness. Saliva samples collected will be transported within 2-3 hours to the lab facilities to be stored under -80 °C temperature. The transportation of these saliva samples will be monitored and carried out by the main researcher.

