3.14.3 Follow up at 1-month and 3-month

Information regarding participant's personal particulars, participant's current chewing status, number of cut-down of habit by the participants (quid/day) and the BQ composition if participants are still chewing will be taken through face-to-face interview with a follow-up questionnaire.

At 3-month, participants' saliva samples will be collected to evaluate the intermediate term effectiveness of the intervention and to verify the self-reported outcomes. The same cut-off levels of AN and cotinine will be used to represent the participant's cessation of their chewing habit.

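### The saliva outcome reads cessation from the follow-up level alone, and entry sets no baseline saliva level, so an infrequent chewer below the cut-offs throughout is scored as ceased without having changed

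*Protocol*

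**What the plan says.** **Entry.** Protocol 3.8 admits "A self-reported BQ chewer who has been chewing BQ for the past 6 months with atleast 2-3 chewing episode per week". Saliva enters the criteria only as a willingness to give samples: participants must "agree to comply with all protocol-specified procedures such as providing saliva samples". No level is required.

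**Baseline sample.** Under 3.14.1, "baseline saliva samples will be gained for biomarker comparison as a method to verify the" self-reported effect. No section says what happens to a participant who is already below the cut-offs at that visit.

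**Follow-up rule.** Section 3.12.2 sets cut-offs of 60 ng/mL for arecoline, 10 for arecaidine, 20 for guvacoline, 6 for guvacine and 10 for cotinine, and states: "Biomarkers level above this cut-off points represent that participants are still practicing the habit and have not ceased the habit". Section 3.14.2 repeats this for Day 22. Section 3.14.3 gives the converse for Month 3: "The same cut-off levels of AN and cotinine will be used to represent the participant's cessation of their chewing habit". The rule uses the level at the visit and contains no change from baseline.

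**Marker lifetime.** Section 2.11 reports from a pharmacokinetic pilot study that the areca alkaloids "peaked within the first 2 hours post-chewing before returning to baseline levels after 8 hours", and concludes that they can be followed only over that short period.

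**Role of saliva.** The primary outcome is self-reported quitting at Day 22 and Month 3 (3.12.1). Saliva is secondary, but it also serves to verify self-report (3.14.2, 3.14.3) and is one of the two measures of effectiveness in objective iv (1.6.2).

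**The concern.** The entry threshold and the saliva rule do not fit together. The rule can detect cessation only in someone whose saliva would have been positive had they gone on chewing. Entry is open to people for whom that is often not so. For them a low value at follow-up carries little information, yet the rule reads it as cessation.

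Two consequences follow. On the saliva outcome taken alone, unchanged chewers are counted as ceased in both arms, which raises both rates and narrows the difference. Where saliva is used to check self-report, a false claim of quitting by such a person is confirmed. Saliva is the trial's only objective check on a self-reported primary outcome. Neither questionnaire (Appendices C and M) asks when the participant last chewed, so an uninformative negative cannot be recognised afterwards.

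**Working it through.** **1. The plan's own figure.** Inputs from 3.4: p1 = 0.3864, p2 = 0.0909, alpha 0.05 (taken as two-sided), power 0.80, ratio 1.

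- Uncorrected: n = [1.960·√(2·0.23865·0.76135) + 0.842·√(0.3864·0.6136 + 0.0909·0.9091)]² / 0.2955² = 31.5, so 32 per arm.
- With continuity correction: n/4·[1 + √(1 + 4/(n·0.2955))]² = 37.9, so 38 per arm and 76 in total, as stated.
- Dropout: 38 × 1.2 = 45.6, so 46 per arm and 92 in total, as stated.

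The sample size does not depend on the present point. It supplies the rates used in step 3.

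**2. Time outside the detection window at the entry minimum.** Inputs: k = 2 or 3 episodes a week (3.8) and a window of at most 8 h (2.11). Share outside = 1 − 8k/H.

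- Whole week, H = 168: k = 2 gives 1 − 16/168 = 90.5%; k = 3 gives 1 − 24/168 = 85.7%.
- Waking hours, H = 16 × 7 = 112: k = 2 gives 1 − 16/112 = 85.7%; k = 3 gives 1 − 24/112 = 78.6%.

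This assumes that the windows do not overlap and that sampling time is unrelated to chewing. The waking-hours version also puts every window wholly within waking time.

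**3. Effect on the saliva outcome.** Let p be the true quit rate and q the share of continuing chewers below the cut-offs at the visit, equal in both arms. The observed saliva rate is p + (1 − p)q, so the difference becomes (p1 − p2)(1 − q). The documents do not give q, so a range is shown.

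| q (assumed) | Intervention | Control | Difference (points) | Power, 38 per arm |
|---|---|---|---|---|
| 0 | 38.6% | 9.1% | 29.6 | 0.87 |
| 5% | 41.7% | 13.6% | 28.1 | 0.79 |
| 10% | 44.8% | 18.2% | 26.6 | 0.71 |
| 20% | 50.9% | 27.3% | 23.6 | 0.56 |
| 30% | 57.0% | 36.4% | 20.7 | 0.44 |
| 50% | 69.3% | 54.5% | 14.8 | 0.26 |

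For q = 10%: 0.3864 + 0.6136 × 0.10 = 0.448 and 0.0909 + 0.9091 × 0.10 = 0.182. In 38 per arm that is 0.9091 × 0.10 × 38 = 3.5 falsely ceased controls and 0.6136 × 0.10 × 38 = 2.3 in the intervention arm. Power uses the two-sided pooled formula without continuity correction and treats participants as independent, as 3.4 does. It concerns an outcome on which the trial was not sized.

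**The case against.** **Saliva is secondary and supports self-report.** This stands, and it limits the point. A reader might infer that a fixed share of each arm would become verified quitters whatever the effect. For example, if a fifth of participants chew at the entry minimum, 0.20 × 85.7% to 0.20 × 90.5% gives 17% to 18%, about twice the planned control rate of 9.09%. The documents do not support this. Verification also needs a report of having quit, so an unchanged chewer who answers honestly is not verified. The one-fifth share has no source, and 3.4 does not say that 9.09% is a saliva rate.

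**A negative result is not certain.** This also stands. Section 2.11 says that levels return to baseline after 8 hours, not that they are then below the cut-offs. Tobacco in the quid is allowed and smokers are not excluded, so cotinine may keep some participants above a listed limit. The protocol does not say whether one marker or all must be low. People chewing several quids daily would mostly test positive. Sampling takes place at organised sessions, not at a random hour.

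**Payment may encourage an overstated habit at entry.** Sessions are incentivised (3.10.3.2), but nothing in the document shows overstatement. This remains conjecture.

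**A baseline comparison is planned, and details belong in an analysis plan.** How to handle baseline-negative samples could be left there. The classification rule, however, is already fixed in 3.12.2 to 3.14.3, and followed as written it gives the wrong answer for these participants.

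**The root cause is the short marker window.** Largely true, which is why the remedy is only partial.

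**Conclusion.** The point holds for the saliva secondary outcome and for its use in confirming self-report. An unchanged infrequent chewer who is below the cut-offs at both visits is scored as ceased, and a false report of quitting by that person would be confirmed. The self-reported primary outcome and the sample size are not affected.

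The size cannot be settled from the document. The 86% to 90% (79% to 86% of waking hours) describes time outside the window at the entry minimum. It is not a predicted negative rate for the trial. Each 10% of continuing chewers who test below the cut-offs removes a tenth of the saliva difference, provided the share is the same in both arms. If it differed between arms, the difference could move either way.

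**What to change.** In 3.12.2, and by reference in 3.14.2 and 3.14.3, replace the follow-up-only rule with a definition along these lines: among participants with at least one areca alkaloid above its cut-off at baseline, saliva-confirmed cessation means that all four areca alkaloids are below their cut-offs at follow-up and the participant reports having quit.

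Alongside it:

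- report the number baseline-negative in each arm and label them not verifiable;
- keep those participants in the self-report primary outcome;
- show the all-participant saliva result as a sensitivity analysis.

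The restriction rests on a sample taken before the first support session, so it does not select on response to the sessions.

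The protocol should state that the remedy is partial. An infrequent chewer who happens to be positive at baseline can still be outside the window at follow-up without having quit. The added self-report condition protects only against those who answer honestly.

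The cost is wording and a smaller secondary denominator, since the baseline saliva is already collected. For instance, if 10% were baseline-negative, 38 per arm would fall to about 34 (38 × 0.9 = 34.2).

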3.0 MATERIALS AND METHOD

3.1 Overview of the Study design

This is a comparative prospective community trial which utilises a cluster randomised controlled trial design involving a Bajau indigenous community in Sabah, Malaysia with a 1:1 allocation ratio. The clusters are Bajau villages that practises BQ chewing habits in Kota Belud district in Sabah. The Bajau villages are the unit of randomisation. There are 39 Bajau villages in Kota Belud, Sabah (Tahir Z et al., 2003).

The clustered randomised controlled trial study design was selected as there was a high tendency of crossover if both intervention and control groups are randomised within the same village. Individuals allocated to a control group may inadvertently receive some aspects of the intervention if they are in proximity to the individuals in intervention group (Hahn S et al (2005). Thus, clustered randomised trial is the best available design for researchers who evaluating intervention that operates at group level, that manipulates the social and physical environment and cannot be delivered to individual participants without any substantial risk of contamination (NIH, 2022).

The eligible villages will be randomised into intervention and control groups based on the required sample size. The intervention group will receive an educational booklet and a structured BQ cessation program which will be cross- culturally adapted first based on a clinical trial (BENIT) by Paulino YC et al. (2020) for a Malaysian high risk population. The control group will only receive an educational booklet.

Baseline information on participant's demographics, BQ chewing behaviours, BQ composition, BQ dependency levels, reasons for chewing, the readiness and self perceived barriers to cease habit will be obtained prior to the commencement of the intervention. The

same participants will be followed-up at 22-day and 3-month after commencement of intervention to assess their of quitting experience and impact of the intervention. Day 22 follow-up was kept in this study as it will enable study results to be compared with similar BQ cessation studies in other parts of the world such as in Pacific Islands (Moss J. et al., 2015 and Paulino YC et al., 2020).

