3.2 Background of Study Location and Population

This study will take place in Kota Belud, Sabah. The state of Sabah has recorded the highest number of BQ chewers in Malaysia (2,283 people). BQ chewers contributed to 16.42% of the total individuals that practiced oral cancer risk habits in Sabah; based on the National Oral Cancer Screening report for the year of 2021, MOH (Table 3.1). Sabah is situated in East Malaysia, forming the northern part of the great island of Borneo. Although there is evidence of Chinese trade from the 7th century onward, Sabah’s trade contacts were confined to the Philippines for centuries in the earlier days.

*Table 3.1 Distribution of Oral Cancer Risk Habits in Malaysia in 2021
(Excerpted from National Oral Cancer Screening Report, MOH – Appendix 3)*

No.	State & Federal Territory	Number with Oral Cancer Risk Habits	Number with BQ Risk Habits	Percentage with BQ Risk Habits (%)
1	Sabah	13,893	2,282	16.42
2	Selangor	6,990	200	2.86
3	Sarawak	1,624	136	8.37
4	Negeri Sembilan	3,222	166	5.15
5	Melaka	2,621	27	1.03
6	Johor	11,096	176	1.59
7	Perak	8,915	420	4.71

8	Kedah	7,676	211	2.75
9	Pulau Pinang	5,172	45	0.87
10	Perlis	1,622	9	0.55
11	Pahang	4,919	461	9.37
12	Kelantan	5,968	47	0.79
13	Terangganu	3,957	50	1.26
14	Kuala Lumpur & Putrajaya	4,936	33	0.67
15	Labuan	479	14	2.92

A further probe into the districts of Sabah revealed that Kota Belud (KB) had the highest number of people practicing the BQ chewing habit. Table 3.2 shows among 1,769 people with oral cancer risk habits in KB, 818 people practised BQ chewing habits (46.24%).

*Table 3.2 Distribution of Betel Quid Users in State of Sabah, Malaysia in 2021
(Excerpted from National Oral Cancer Screening Report, MOH – Appendix 3)*

No.	District Names	Number With Oral Cancer Risk Habits	Number With BQ Risk Habits	Percentage With BQ Risk Habits (%)
1	Kota Belud	1,769	818	46.24
2	Keningau	2,883	607	21.05
3	Kudat	2,038	369	18.11
4	Beaufort	1,102	232	21.05
5	Kota Kinabalu	2,311	132	5.71
6	Sandakan	1,863	97	5.21
7	Penampang	130	11	8.46
8	Tawau	1,330	8	0.60
9	Lahad Datu	467	8	1.71

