Kota Belud is located at west coast of Sabah and was one of the first administrative district in Sabah during British occupation. It is located 70km from Kota Kinabalu, the capital of Sabah. The district has an area of 1,391 square kilometres and a population of 107,243 people (Department of Statistics, Malaysia, 2020). The three main ethnicities in Kota Belud are Bajau, Dusun dan Irranun. There is also a minority of Chinese in this district.

The gender distribution in this district is equal; 50.3% of males and 49.7% of females. Close to two-thirds of the population are between 15-64 years old (64.1%), followed by 30% who are between age 0-14 years old and a small percentage are above 65 years old (5.9%). Most of the population are Muslim, followed by Christianity and Buddhism and others.

The population of interest for this study in Kota Belud is the Bajau community. The Bajaus, are one of the indigenous groups in Sabah that still practises their traditional culture. They are often referred to as “cowboys of the east” as their lifestyle resembles the lifestyle of western cowboys. Their main language for communication is Malay, but the older generation are more familiar in their Bajau dialect. There are 134 villages in Kota Belud and 39 villages of it were dominated by Bajau people (Tahir Z et al., 2003).

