3.5 Sampling and randomisation method

Prior to randomisation, matching of eligible Bajau villages will be carried out to increase precision and to minimise imbalance across intervention and control groups. This study involves 2 levels of randomisation. The randomisation sequence will be carried out by statistician employed at Faculty of Dentistry, Universiti Malaya.

At the first level of randomisation, all eligible Bajau villages from the total 39 Bajau villages will be paired according to location and average number of BQ chewers in the village (Figure 3.2).

At the second level of randomisation, computer generated random numbers will be used to randomly allocate the Bajau villages in each matched-pair to intervention and control groups. The match-pairs will be randomly selected until the sample size is met.

Bajau villages matched according to average number of BQ chewers in the village

Figure 3.2 Diagram depicting Flow of Matching of Clusters in the Study

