3.6 Allocation concealment

In this study, allocation concealment will be done at cluster level. A senior dental officer (SDO) in Kota Belud Dental District Office who is not involved in cluster identification and recruitment will keep the allocation sequence in a brown envelope in his or her SDO's office until the matched pair are ready to be recruited into the study.

The allocation sequence will be generated by a statistician employed at the Faculty of Dentistry, Universiti Malaya using computer generated tables. The information will be kept confidential until the intervention are assigned to the villages.

Within the cluster, a universal sampling technique will be used to recruit participants into the study. Universal sampling is also known as a total population sampling; which is a type of purposive sampling that involves examining the entire population that have a particular set of characteristics (Laerd Statistics, 2012). All eligible participants who fulfilled the inclusion and exclusion criteria through the screening session will be recruited as study sample. Thereafter, informed consent will be obtained from the participants.

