3.10.3 Phase 3 Implementation of the study (Field Work)

3.10.3.1 Initiatives to promote study

Prior to the start of the intervention, a **promotional initiative** will be conducted with the village head 3 weeks before the implementation of the study. The purpose of this promotion is to provide knowledge and convince the village head regarding the ill effects of the chewing habit. By agreeing and cooperating to this intervention, his villagers will receive the very first kind of such an intervention in Malaysia to curb the villager's 'addiction'. With adequate knowledge and a right attitude, the village head can have a positive predisposition to encourage his villagers to participate in this beneficial program. Once the trust of the 'strongman (the village head) has been gained', it will be easier to conduct the multi-component intervention in those villages.

Attractive posters and flyers will be distributed to the village head to paste in the allowed public places and for door-to-door flyer dissemination to ensure the villagers are aware of the intervention on the said date. The intervention will be carried on a weekend to obtain maximum participation.

One week before the implementation of the study, villages will be reminded of the program date and villagers who practises BQ habits will be advised to attend the intervention together with family members, relatives or neighbours who also has the similar habit. Moss J et al. (2015) claimed intervening the surrounding community with the similar risk habits can ensure the long term sustainability of habit cessation among chewers.

The first day of the program will be the screening day.

[figure not shown]
[figure not shown]

Figure 3.5 Summary of Promotional Initiatives

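### Residence is required only at district level although villages are randomised, which leaves a route of unknown size for people to enrol in the arm of a village they do not live in

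*Protocol*

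**What the plan says.** Four parts of the Protocol bear on who belongs to which arm.

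- **Unit and reason.** Section 3.1 states: "The Bajau villages are the unit of randomisation". It chose clusters because of contamination: "Individuals allocated to a control group may inadvertently receive some aspects of the intervention if they are in proximity to the individuals in intervention group".
- **Eligibility.** Section 3.8 has one residence criterion: "Participants must be residing in study location (Kota Belud, Sabah". Section 3.2 confirms that the study location is the district ("This study will take place in Kota Belud, Sabah") and gives its make-up: "There are 134 villages in Kota Belud and 39 villages of it were dominated by Bajau people".
- **Recruitment.** Section 3.6 describes universal sampling inside the cluster, then gives the operating rule: "All eligible participants who fulfilled the inclusion and exclusion criteria through the screening session will be recruited as study sample". In section 3.10.3.2, attendees at the community hall are registered and screened for eligibility at Checkpoint 1. No check of village is described, and nothing is said about an attendee who lives elsewhere.
- **Invitation.** Under section 3.10.3.1, chewers are "advised to attend the intervention together with family members, relatives or neighbours who also has the similar habit". No village limit is attached.

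Two further details matter. Section 3.6 keeps the allocation sealed only until a matched pair is ready for recruitment, so the arm may be known before individuals enrol. Section 3.10.3.2 describes payment for each session attended in the intervention arm, while at screening control participants are described as receiving a token of appreciation.

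**The concern.** In a cluster trial, a participant's arm should follow from the village he or she belonged to before allocation was known. Here the written criteria do not make that link. A chewer from an unselected village, or from a village in the other arm, who accompanies a relative to a screening session can satisfy every listed criterion.

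Two things are at stake. The first is selection: people motivated to quit, or drawn by paid sessions, could join an intervention village from outside and raise its quit rate for reasons unrelated to the program. The second is crossover: a person who lives among intervention participants could be enrolled in a control village, which is the contamination the design was chosen to avoid.

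The route is foreseeable from the Protocol's own literature review. Section 2.7 reports that in an earlier cognitive-behavioural cessation program, incentives drew in extended family, relatives arrived by shared car without appointments, and the program became walk-in. This trial combines incentives, a family invitation and open hall screening.

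**Working it through.** **Step 1. Compare the levels at which the rules operate.**

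| Element | Level | Section |
|---|---|---|
| Randomisation | village | 3.1, 3.5 |
| Sampling intent | cluster (village) | 3.6 |
| Residence criterion | district, 134 villages | 3.8, 3.2 |
| Invitation to relatives and neighbours | no limit stated | 3.10.3.1 |
| Village check at Checkpoint 1 | none described | 3.10.3.2 |
| Home address | recorded, but no rule uses it | Appendix C |

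The intent is at village level. The criterion that staff would apply is at district level. No later step closes the gap.

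**Step 2. Confirm the planning rates (section 3.4).** Inputs: p1 = 0.3864, p2 = 0.0909, alpha 0.05 (taken as two-sided), power 0.80. The difference is d = 0.3864 − 0.0909 = 0.2955.

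- n = [1.960·√(2·0.23865·0.76135) + 0.842·√(0.3864·0.6136 + 0.0909·0.9091)]² / 0.2955² ≈ 31.5, so 32 per arm.
- With continuity correction: (31.46/4)·[1 + √(1 + 4/(31.46·0.2955))]² ≈ 37.9, so 38 per arm and 76 in total.

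This matches the Protocol, so the rates below are the ones it planned on.

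**Step 3. Self-selection with no program effect (illustrative).** Let a share g of the intervention arm be outsiders who quit at rate h, with residents and controls quitting at 0.0909. The spurious difference is g·(h − 0.0909).

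| g | h = 0.30 | h = 0.50 |
|---|---|---|
| 10% | 0.021 | 0.041 |
| 20% | 0.042 | 0.082 |
| 30% | 0.063 | 0.123 |

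In an arm of 46 this runs from 46 × 0.021 ≈ 1 to 46 × 0.123 ≈ 6 extra quitters. Both g and h are assumptions; the Protocol gives neither.

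**Step 4. Crossover into control (illustrative).** Let a share f of controls quit at the full intervention rate. The difference becomes (1 − f) × 29.55 points: 26.6 points at f = 10% and 23.6 at f = 20%. Power at 38 per arm (pooled z test, no continuity correction, clustering ignored) falls from 0.87 to 0.77 and 0.65. Only the part of f that comes from enrolment in the wrong village is due to this criterion.

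**The case against.** The strongest reply is that recruitment by village is already stated. Section 3.6 puts sampling inside the cluster, section 3.1 says the clusters are villages, and sections 3.10.3.1 and 3.10.3.2 speak of villagers throughout, with promotion through the village head and door-to-door flyers. On this reading the section 3.8 criteria apply only within the village. Neighbours will mostly be co-residents, and the other criteria (a regular chewer, able to use Bajau, willing to quit, agreeing to five sessions) make the pool of possible outsiders far smaller than the district population.

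Much of this stands. It establishes intent and suggests that the numbers may be small. It does not say who counts as a member of the cluster, who checks, or what happens to a relative from elsewhere who passes the list.

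Three stronger readings should be resisted:

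- A reader might infer that village randomisation no longer protects the comparison. The documents do not support this: villages remain the randomised unit, and no volume of cross-village enrolment is given.
- A reader might infer from "all eligible Bajau villages from the total 39 Bajau villages will be paired according to location and average number of BQ chewers in the village" that paired villages adjoin. Location is not defined there and no distances are given, so this is conjecture.
- A reader might attribute all dilution to the criterion. Content passed between relatives in different villages would continue under a village-level rule; it is a general limit of cluster trials.

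**Conclusion.** The point holds as a defect in how cluster membership is put into operation. The residence criterion is set at a wider level than the randomised unit, the invitation has no village limit, and no check connects a participant to a village. The size of the resulting bias cannot be known from the documents. Under the stated assumptions (10 to 30% outsiders quitting at 30 to 50%), self-selection alone would produce about 2 to 12 points, against a planned difference of 29.55 points.

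It should be settled before recruitment because analysis cannot fully repair it. Outsiders enrolled under a valid criterion could be removed only by post-randomisation exclusion. Analysis by village of residence could help for people from another trial village, but those from villages outside the trial have no randomised arm.

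**What to change.** 1. **Section 3.8.** Replace district residence with usual residence in the randomised village, as of a date before the pair's allocation is released.
2. **Section 3.10.3.2, Checkpoint 1, both arms.** Check village of residence at registration. Appendix C already records current home address; take that item at Checkpoint 1 rather than leaving it to the interview at Checkpoint 2, and add how long the person has lived there.
3. **Section 3.10.3.1.** Limit the invitation to family and neighbours living in the same village.
4. **Section 3.6 or 3.8.** State that non-residents who attend may receive the booklet but are not enrolled, and log how many there were in each village.

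The cost is a few lines of text, one short question at registration and some walk-in volunteers turned away. No condition on the distance between paired villages is needed for this point.
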